2. TYPE OF PLANNED ANALYSIS

2.1. Data Monitoring Committee Analysis

An external multidisciplinary Data Monitoring Committee (DMC) will review the progress of the study and perform interim reviews of safety data in order to protect subject welfare and preserve study integrity. The DMC is to recommend to the sponsor whether the nature, frequency, and severity of adverse effects associated with study treatment warrant the early termination of the study in the best interests of the participants, whether the study should continue as planned, or whether the study should continue with modifications.

Three safety reviews are expected to be required after approximately 25%, 50%, and 75% of the planned 200 subjects are enrolled and complete Day 28 visit or discontinue the study. The regularity of such reviews may also be determined by enrollment rates and evidence of potential safety concerns. Additional reviews may be conducted at the request of the DMC or the sponsor. At each review, all available safety data will be summarized and evaluated.

The DMC's role and responsibilities and the scope of analysis to be provided to the DMC are provided in a mutually agreed upon charter, which defines the DMC membership, meeting logistics, and meeting frequency.

2.2. Efficacy Interim Analysis

Three efficacy interim analyses are currently planned for administrative purposes by the internal Gilead staff. These analyses will be performed when approximately 25%, 50% and 75% of the planned 200 subjects are enrolled and complete Day 28 of the study, respectively. A Haybittle-Peto boundary will be used for the alpha spending with an overall alpha of 0.00001 for each interim analysis and overall alpha of 0.05 for the final analysis.

This study will not be stopped early for efficacy based on the interim efficacy analysis results. The purpose of these analyses is to obtain an early assessment of the effect of presatovir. The interim efficacy results will aid internal decision-making on the further development of the presatovir program. If the results are sufficiently positive or informative, the data may be used to plan other Phase 2 and 3 studies, to seek guidance from FDA on the program development in the different subject populations, including the partial clinical hold for the pediatric program.

A Gilead Executive Team including the Vice President (VP) of Clinical Research and the VP of Biometrics will review the unblinded interim efficacy analysis results. Based on this information, the GSI Executive Team will make a decision on whether the results are informative to use in the planning of other Phase 2 and 3 studies, whether to include the results in the response to the FDA on the partial clinical hold for the pediatric program. A GSI unblinded team that is independent of the GS-US-218-0108 Study Team may be formed to support the decisions of the GSI executive team, if needed. This unblinded team will include representatives from Gilead Clinical Research, Biometrics, Regulatory Affairs, and Medical Writing groups who are not directly associated with Study GS-US-218-0108.

The GS-US-218-0108 Study Team will remain blinded to treatment assignments throughout the trial until all subjects have completed the planned study visits and the database has been locked and unblinded.

As of the finalization of this SAP, 2 efficacy interim analyses have been performed in May 2016 and September 2017 after 25% and 75% of the subjects enrolled. An alpha level of 0.00001 was used at each interim analysis using the Haybittle-Peto boundary, and the final analysis will be performed at a 0.05 level of significance.

2.3. Final Analysis

After all subjects have completed the study, outstanding data queries have been resolved, and the database has been cleaned and finalized, the study blind will be broken and the final analysis of the data will be performed.

The efficacy analysis of the co-primary and secondary endpoints will be conducted at the overall significance level of 0.05. The fallback procedure {Wiens 2005} will be applied to test the co-primary and secondary endpoints sequentially as described in Section 3.5.

3. GENERAL CONSIDERATIONS FOR DATA ANALYSES

3.1. Analysis Sets

Analysis sets define the subjects to be included in an analysis. Analysis sets and their definitions are provided in this section. Subjects included in each analysis set will be determined before the study blind is broken for analysis. The analysis set will be identified and included as a subtitle of each table, figure, and listing.

For each analysis set, the number and percentage of subjects eligible for inclusion, as well as the number and percentage of subjects who were excluded and the reasons for their exclusion, will be summarized by treatment group.

A listing of reasons for exclusion from analysis sets will be provided by subject.

3.1.1. All Randomized Analysis Set

All Randomized Analysis Set includes all subjects who were randomized in the study.

3.1.2. Full Analysis Set

The Full Analysis Set (FAS) includes all randomized subjects who took at least 1 full dose of study drug, and had an RSV viral load greater than or equal to the lower limit of quantification (LLOQ) of the RT-qPCR assay in the Day 1 nasal sample, as determined by RT-qPCR at the central lab. This is the primary analysis set for efficacy analyses.

3.1.3. Per Protocol Analysis Set

The Per-Protocol (PP) Analysis Set includes subjects in the FAS who meet the following criteria:

- Did not violate any major inclusion criteria (IC) or exclusion criteria (EC)
 - IC: Received an autologous or allogenic HCT
 - IC: Documented RSV-positive ≤ 6 days prior to Day 1
 - IC: Had respiratory symptoms ≤ 7 days prior to Day
 - IC: Had evaluable baseline chest image (ie, had evidence of new abnormalities consistent with LRTI on chest X-ray; had chest X-ray taken ≤ 48 hours prior to screening)
- Did not have IMP overdose that resulted in an AE
- Did not take invalid (expired, damaged, quarantined, improperly stored, etc) drug
- Was not dispensed incorrect study drug (wrong bottle, drug from another study, etc)

- Missed < 1 dose within the first 9 study days
- Missed < 3 nasal swabs over the course of the study
- Did not receive any prohibited concomitant medications

The specific classification of subjects to be included in the PP analysis set will be finalized prior to database lock. Subjects will be grouped according to the treatment they actually received. This analysis set is to be used for sensitivity analysis of the co-primary and secondary endpoints.

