- 1) Adult males and females 18 to 75 years of age. In Japan subjects must be 20 to 75 years of age. In Singapore subjects must be 21 to 75 years of age.
- 2) Received an autologous or allogeneic HCT using any conditioning regimen
- 3) Documented to be RSV-positive as determined by local testing (eg, polymerase chain reaction [PCR], direct fluorescence antibody [DFA], respiratory viral panel (RVP) assay, or culture) using an upper respiratory tract sample collected ≤ 6 days prior to Day 1, or as determined at Screening as per Section 6.1.1.
- 4) New onset of at least 1 of the following respiratory symptoms for ≤ 7 days prior to Day 1: nasal congestion, runny nose, cough, or sore throat, or worsening of one of these chronic (associated with a previously existing diagnosis, eg, chronic rhinorrhea, seasonal allergies, chronic lung disease) respiratory symptoms ≤ 7 days prior to Day 1
- 5) No evidence of new abnormalities consistent with LRTI on a chest X-ray relative to the most recent chest X-ray, as determined by the local radiologist. If a chest X-ray is not available or was not obtained during standard care < 48 hours prior to Screening, a chest X-ray must be obtained for Screening
- 6) Oxygen saturation $\geq 92\%$ on room air
- 7) An informed consent document signed and dated by the subject or a legal guardian of the subject and the investigator or his/her designee. In Sweden ICFs signed by a legal guardian must also be signed by a close relative of the subject.

- 8) A negative urine or serum pregnancy test is required for female subjects (unless surgically sterile or greater than two years post-menopausal)
- 9) Male and female subjects of childbearing potential must agree to contraceptive requirements as described in [Appendix 5](#)
- 10) Willingness to complete necessary study procedures and have available a working telephone or email

Exclusion Criteria

Subjects who meet *any* of the following exclusion criteria are not to be enrolled in this study.

Related to concomitant or previous medication use:

- 1) Use of non-marketed (according to region) investigational agents within 30 days, **OR** use of any investigational monoclonal anti-RSV antibodies within 4 months or 5 half-lives of Screening, whichever is longer, **OR** use of any investigational RSV vaccines after HCT

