4.2. Inclusion Criteria

Subjects must meet all of the following inclusion criteria to be eligible for participation in this study.

- 1) Adult male and female subjects 18 to 75 years of age. In Japan subjects must be 20 to 75 years of age. In Singapore subjects must be 21 to 75 years of age.
- 2) Received an autologous or allogeneic HCT using any conditioning regimen
- 3) Documented to be RSV-positive as determined by local testing (eg, PCR, DFA, RVP assay, or culture) using an upper respiratory tract sample collected ≤ 6 days prior to Day 1, or as determined at Screening as per Section 6.1.1
- 4) New onset of at least 1 of the following respiratory symptoms for ≤ 7 days prior to Day 1: nasal congestion, runny nose, cough, or sore throat, or worsening of one of these chronic (associated with a previously existing diagnosis, eg, chronic rhinorrhea, seasonal allergies, chronic lung disease) respiratory symptoms ≤ 7 days prior to Day 1
- 5) No evidence of new abnormalities consistent with LRTI on a chest X-ray relative to the most recent chest X-ray, as determined by the local radiologist. If a chest X-ray is not available or was not obtained during standard care < 48 hours prior to Screening, a chest X-ray must be obtained for Screening
- 6) O_2 saturation $\geq 92\%$ on room air
- 7) An informed consent document signed and dated by the subject or a legal guardian of the subject and the investigator or his/her designee. In Sweden ICFs signed by a legal guardian must also be signed by a close relative of the subject.
- 8) A negative urine or serum pregnancy test is required for female subjects (unless surgically sterile or greater than two years post-menopausal)
- 9) Male and female subjects of childbearing potential must agree to contraceptive requirements as described in [Appendix 5](#)
- 10) Willingness to complete necessary study procedures and have available a working telephone or email

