6.2.1. Time-Weighted Average Change in Nasal RSV Viral Load

The treatment difference in the time-weighted average change from Baseline (Day 1) to Day 9 in nasal RSV viral load (\log_{10} copies/mL) will be analyzed using a parametric ANCOVA with the baseline viral load (\log_{10} copies/mL) and stratification factors as covariates in the model. The test will be 2-sided with the significance level of 0.01. Nonparametric methods such as rank-based ANCOVA models or Wilcoxon rank sum tests may be implemented for exploratory purposes.

Adjusted means for each treatment group, 99% confidence interval (CI), and descriptive statistics (sample size, mean, SD, median, Q1, Q3, minimum, and maximum) will be presented in the descriptive summaries. Missing viral load data will be handled using the method described in Section 3.6.

6.2.2. Proportion of Subjects Who Develop a LRTC through Day 28

The proportion of subjects who develop a LRTC through Day 28 will be analyzed using a 2-sided Cochran-Mantel-Haenszel test stratified by the randomization stratification factors. The significance level used for the analysis (eg, 0.04 or 0.05) will be determined based upon the decision to reject the null hypothesis of the other co-primary endpoint as described in Section 3.5. The 2-sided 95% CI for the odds ratios between the 2 treatment groups will be constructed based on stratum-adjusted Mantel-Haenszel proportions.

The numbers and percentages of subjects who develop a LRTC through Day 28 will be provided with 95% CIs for the percentages based on the Clopper-Pearson method {Clopper 1934}.

The final analysis will be performed when all randomized subjects either complete Day 28 assessments or discontinue study prematurely.

The analyses of the co-primary endpoints will be repeated using the PP analysis set.

The primary efficacy analyses will also be repeated for the subgroups specified in Section 3.4, including the stratification factors (presence or absence of lymphopenia, treatment of RSV infection with ribavirin [yes or no] prior to randomization, sex, race, age group [< 65 or ≥ 65], type of transplant [autologous HCT or allogeneic HCT]. Adjusted mean and 95% CI will be presented by treatment group for exploratory purposes.

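### The chest-image item in the per-protocol definition (SAP 3.1.3) has lost its 'no' and contradicts both inclusion criterion 5 and the bullet it sits under

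*SAP*

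**What the plan says.** SAP 3.1.3 opens with the rule for membership: "The Per-Protocol (PP) Analysis Set includes subjects in the FAS who meet the following criteria". The first condition is "Did not violate any major inclusion criteria (IC) or exclusion criteria (EC"), and beneath it are four sub-items marked IC. Three are plain requirements, for example "IC: Received an autologous or allogenic HCT". The fourth is the imaging item. It calls for an evaluable baseline chest image and explains this, after an 'ie' in parentheses, as meaning that the subject "had evidence of new abnormalities consistent with LRTI on chest X-ray". The same parenthesis adds that the film was taken no more than 48 hours before screening.

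Protocol 4.2, inclusion criterion 5, reads: "No evidence of new abnormalities consistent with LRTI on a chest X-ray relative to the most recent chest X-ray". The synopsis repeats it, and Protocol 3.2 describes the randomized population as having upper-tract symptoms without lower-tract infection. On timing, criterion 5 accepts a standard-care film from less than 48 hours before Screening and otherwise requires one for Screening.

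The PP set has a stated use. SAP 6.2.2 says "The analyses of the co-primary endpoints will be repeated using the PP analysis set", and SAP 6.3.3 names the PP set for the sensitivity analysis of the secondary endpoint.

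**The concern.** An analysis-set definition is a rule that a programmer executes. Here the rule asks for the finding that should have kept a subject out of the trial. If it were followed as printed, the PP analyses would be empty or would rest on the wrong subjects. If it were quietly corrected in code, the reported PP analysis would no longer match the prespecified definition.

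Three planned outputs depend on it: PP Tables 15.9.1.1.2 (viral load), 15.9.1.2.2 (lower respiratory tract complication, LRTC) and 15.9.2.1.2 (respiratory failure or death). For the secondary endpoint, the PP analysis is the only sensitivity analysis that SAP 6.3.3 names.

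**Working it through.** The plan gives no figure to reproduce on this point. The check is a comparison of texts, followed by a count for scale.

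**1. Is the item a condition to satisfy or a list of violations?** It is a condition. The set consists of subjects who meet the listed criteria. The sibling items (transplant received, RSV-positive, symptomatic) are all things a subject should have. The second half of the same parenthesis, the film timing, is also a requirement.

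**2. Could it mean only that the film was readable?** The wording does not allow it. The 'ie' equates an evaluable image with the presence of new abnormalities.

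**3. The texts side by side**

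| Source | Finding on the baseline film |
|---|---|
| Protocol 4.2 and synopsis, criterion 5 | no new LRTI-type abnormality |
| Protocol 3.2, study design | no evidence of LRTI |
| Protocol 6.1.1, screening | subjects with new LRTI signs may screen fail and move to study GS-US-218-1502 |
| SAP 3.1.3, parent bullet | no breach of a major criterion |
| SAP 3.1.3, imaging item | new LRTI-type abnormality present |

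Four entries agree and one is reversed. No readable part of the SAP corrects it. SAP 6.5 (changes from protocol-specified efficacy analyses) is blacked out and cannot be used either way.

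**4. The literal result.**
- A FAS subject with new abnormalities breaches criterion 5, which the SAP lists here among the major criteria, and so fails the parent bullet.
- A FAS subject without them fails the imaging item.
- With both applied, no subject qualifies.
- With the imaging item applied alone, only subjects who breach criterion 5 remain.

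**5. Scale.** Let q be the share of subjects with new abnormalities on the baseline film. The documents do not give q, so the values below are assumptions. The enrolled number is 189 (SAP 1.3). The upper bound for the PP set is 189 × q with the item applied alone, and 189 minus that number with 'no' restored.

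| Assumed q | 189 × q | Item alone, at most | 'No' restored, at most |
|---|---|---|---|
| 0% | 0 | 0 | 189 |
| 1% | 1.89 | 2 | 187 |
| 2% | 3.78 | 4 | 185 |
| 5% | 9.45 | 9 | 180 |
| 10% | 18.9 | 19 | 170 |

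These are upper bounds. PP members come from the FAS, which cannot exceed 189, and the other PP conditions remove more. With the parent bullet also applied, the third column is 0 throughout.

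**6. Timing.** The SAP uses ≤ 48 hours and the protocol < 48 hours, so they differ for a film at exactly 48 hours. The SAP also does not mention a film obtained for Screening, although such a film can be read as zero hours before it.

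**The case against.** The strongest reply is that the intent is plain. The item is labelled as an inclusion criterion and sits under a bullet about not violating such criteria, so a careful programmer would read it as compliance with criterion 5. This stands as to intent. It does not make the printed rule correct.

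The second reply is that the plan has safeguards. Analysis sets are fixed before the blind is broken (SAP 3.1) and PP membership before database lock (SAP 3.1.3). Exclusions are tabulated with reasons, and Listing 16.2.3.2 shows FAS subjects left out of the PP set. An empty set would be noticed. The revision log (SAP 11) also says that 3.1.3 was updated to align with an amendment that is not among the documents, and the working criteria may be right there. This stands too, and it means that nothing can be said about how the set was actually derived.

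Three stronger readings are tempting, and the documents do not support them:
- **The definition keeps ineligible subjects.** The parent bullet removes anyone who breaches criterion 5, so the full literal text keeps nobody.
- **Nearly all 189 subjects were lost from the PP analysis.** The documents contain no count of baseline abnormalities and no derived PP set.
- **An LRTC endpoint would have no meaning in subjects with an abnormal baseline film.** Criterion 5 concerns a local reading of findings consistent with infection. The endpoint is adjudicated from wider clinical data and includes bacterial and unusual-pathogen infections that could arise later.

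The timing difference is minor, as the reply would say.

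**Conclusion.** The imaging item in SAP 3.1.3 is wrong as written. It reverses inclusion criterion 5 and contradicts its own parent bullet. Taken literally with that bullet, the PP set is empty; the 0 to 19 range applies only if the item is read alone and rests on the assumed 0 to 10% share.

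The reach is limited to the PP analyses of the two co-primary endpoints and the secondary endpoint. The hypothesis tests use the FAS (SAP 3.1.2, 6.2 and 6.3.2), and the fallback procedure in SAP 3.5 makes no use of the PP set. No primary estimate, p-value or alpha level changes. A reader might infer a threat to the primary conclusion; there is none. That the cause is a dropped word is an inference from the surrounding text, though a strong one.

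**What to change.** Reword the item so that it requires an evaluable baseline chest image that meets criterion 5 in the protocol's own terms, "No evidence of new abnormalities consistent with LRTI on a chest X-ray". In the same line, replace the timing with the protocol's: a film from less than 48 hours before Screening, or one obtained for Screening. Then check the PP derivation program and the draft exclusion listing against the corrected text before database lock.

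If the database is already locked, state in the clinical study report which rule was applied; SAP 1 already requires changes made after SAP finalization to be documented there.

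The cost is one line of SAP text and one program check. No new data, subjects or analyses are needed.

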3.1.4. Safety Analysis Set

The Safety Analysis Set includes subjects who received at least 1 dose of study medication. This is the primary analysis set for safety analyses.

3.1.5. Pharmacokinetic Analysis Set

The Pharmacokinetic (PK) Analysis Set includes all subjects who have been administered at least 1 dose of investigational drug and have at least 1 nonmissing postdose concentration value for presatovir in plasma. This is the primary analysis set for PK summary tables and figures.

PK Substudy Set includes subjects in the PK Analysis Set who elect to participate in extensive PK sampling at the time of informed consent.

3.2. Subject Grouping

For analyses based on the FAS, subjects will be grouped according to the treatment to which they were randomized. For analyses based on the PP and Safety Analysis Sets, subjects will be grouped according to the randomized treatment except when their actual treatment differs from randomized treatment for the entire treatment duration. In this case, subjects will be grouped based on actual treatment received. For the analyses based on the PK Analysis Set, subjects will be grouped according to the actual treatment they received.

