3.4. Duration of Treatment

The treatment portion of the study is 17 days (a total of 5 doses administered as single doses on Days 1, 5, 9, 13, and 17).

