5.2.2. Packaging and Labeling

Presatovir tablets and matching placebo are packaged in white, high density polyethylene (HDPE) bottles with desiccant and polyester fiber coil. Each bottle contains 4 tablets and is capped with a white, continuous thread, child-resistant polypropylene screw cap fitted with an induction-sealed, aluminum-faced liner.

All labels for IMP distributed to investigative sites in the US and the rest of world (ROW) will meet all applicable requirements of the US Food and Drug Administration (FDA), the EU Annex 13 of Good Manufacturing Practices: Manufacture of investigational medicinal products (July 2010), and/or other local regulations, as applicable.

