8.6. Safety Analysis

All safety data collected on or after the date that IMP was first dispensed up to the date of last dose of IMP through Day 28 will be summarized by treatment group (according to the IMP received). Data for the pretreatment and treatment-free follow-up periods will be included in data listings only. Data for the treatment period will be summarized by treatment (active or placebo) using the number of subjects (n and percent) with events/abnormalities for categorical data and using descriptive statistics for continuous data.

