7.7. Changes From Protocol-Specified Safety Analyses

No changes from protocol-specified safety analyses.

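### SAP 3.2 leaves a placebo subject who received some presatovir doses in the placebo column of the safety tables, although Protocol 8.6 groups safety data by product received and SAP 7.7 declares no change

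*SAP*

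**What the plan says.** SAP 3.2 covers the Safety Analysis Set and the Per Protocol (PP) set with one rule: "subjects will be grouped according to the randomized treatment except when their actual treatment differs from randomized treatment for the entire treatment duration". Only then does it switch: "In this case, subjects will be grouped based on actual treatment received".

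Protocol 8.6 starts from the opposite default. Safety data "will be summarized by treatment group (according to the IMP received", and nothing there depends on how long the product received differed from the one assigned. SAP 7.7 says: "No changes from protocol-specified safety analyses".

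Three other places bear on the point:

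- SAP 3.1.4: "The Safety Analysis Set includes subjects who received at least 1 dose of study medication". Subjects given the wrong product are not removed.
- SAP 3.1.3, on the PP set: "Subjects will be grouped according to the treatment they actually received". There is no duration condition here, but the same section excludes subjects who were dispensed incorrect drug.
- Protocol 3.4 describes "a total of 5 doses administered as single doses on Days 1, 5, 9, 13, and 17", and Protocol 5.2.2 states "Each bottle contains 4 tablets".

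**The concern.** The protocol's default for safety is the product received, and the SAP's is the randomised arm. The SAP leaves its default only when the wrong product was taken throughout. Dosing consists of five separate administrations, so a subject can receive both products, and such a subject stays in the randomised column.

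The case that matters is a placebo-randomised subject who received presatovir at some visits. If presatovir causes an event in that subject, the event is tabulated under placebo. Safety is a secondary objective of the trial, and SAP Section 11 says the cardiac events of interest were added to meet an FDA monitoring requirement. Those are low-count tables, where a single misplaced case can be seen. Because SAP 7.7 reports no change, a reader of the clinical study report would have no reason to suspect that the columns are not by product received.

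**Working it through.** The documents give no figure to reproduce. The check is a comparison of rules, followed by the weight of one subject.

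**1. One bottle is one dose.** A dose is 200 mg in 50 mg tablets (Protocol 3.3): 200 / 50 = 4 tablets. A bottle holds 4 tablets (Protocol 5.2.2). A single wrong bottle can therefore affect one visit and leave the other four correct.

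**2. The two rules side by side.** Take a placebo-randomised subject who takes all five doses:

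| Presatovir doses received | Presatovir amount | SAP 3.2 safety column | Product received (Protocol 8.6) |
|---|---|---|---|
| 0 of 5 | 0 mg | Placebo | Placebo |
| 1 to 4 of 5 | 200 to 800 mg | Placebo | Both; no explicit rule |
| 5 of 5 | 1000 mg | Presatovir | Presatovir |

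The documents agree in the first and last rows. In the middle row the SAP assigns placebo to someone who took up to four presatovir doses. The protocol's principle points to receipt but does not say how to resolve it.

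A subject who stops early is treated differently. If the only dose taken came from a wrong bottle, the actual treatment differed throughout on the natural reading of SAP 3.2, and the subject is regrouped. The affected group is therefore those who received presatovir at some but not all of the doses they took.

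**3. Weight of one subject.** SAP 1.3 gives 189 enrolled with 1:1 allocation. Assume an even split and that nearly all were dosed: 189 / 2 = 94.5 per arm.

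- One subject with an event: 1 / 94.5 = 1.06%, about 1.1 percentage points of placebo incidence.
- At the planned 100 per arm: 1 / 100 = 1.0 point.
- The number of such subjects is not given. For an assumed 0 to 3 with events, the range is 0 to 3 / 94.5 = 3.2 points.

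**4. A rare event.** Suppose the only case of some cardiac event falls in such a subject. The SAP table shows presatovir 0, placebo 1. Grouping any presatovir exposure as presatovir shows 1 and 0. This illustrates the mechanism; it is not a forecast.

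**The case against.** The strongest reply is that Protocol 8.6 says nothing about a subject who received both products. Where the wrong product was taken throughout, the SAP and protocol agree. For mixed exposure, the SAP may be said to fill a gap. This stands in part: a reader might infer that the SAP breaks an explicit protocol rule placing such subjects under presatovir, and there is no such rule. What remains is that the SAP fills the gap by reverting to the randomised arm, against the protocol's stated principle, without declaring it.

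Other inferences also go further than the documents allow:

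- *That dispensing errors are expected, typically one bottle at one visit.* Bottle contents make this possible. How bottles are assigned across visits is not shown, and a planned listing of subjects given the wrong drug (16.2.2.4) does not show that any error was expected.
- *That the same person is presatovir for PK and placebo for safety.* SAP 3.2 groups the PK set by actual treatment but is equally silent on mixed exposure.
- *That the opposite error is harmless.* A presatovir subject given some placebo bottles stays under presatovir with less exposure, which also dilutes risk. The proposed rule does not change that.
- *That the PP analyses are affected.* SAP 3.1.3 already removes subjects dispensed incorrect drug, so the disagreement between 3.1.3 and 3.2 has almost no one to act on.

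It is also fair that the laboratory, vital sign, troponin and ECG displays carry no formal testing, and that affected subjects could be traced through the wrong-drug, drug administration and adverse event listings. The listings do not regroup anyone in the tables, however, and the tables are what most readers use.

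**Conclusion.** The concern holds in a limited form. SAP 3.2 defaults the Safety Analysis Set to the randomised arm where Protocol 8.6 groups by product received, and SAP 7.7 does not disclose it. A placebo-randomised subject with partial presatovir exposure is counted as placebo in every safety table.

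The size is about 1.1 percentage points of placebo incidence per such subject with an event, assuming about 94.5 dosed subjects per arm. It dilutes a presatovir signal only if the event was caused by presatovir. The number of affected subjects is unknown and may be zero, in which case no result changes and only the inconsistency in the text remains. The expected effect is small, but the change costs little and the rule should be settled before unblinding.

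**What to change.** In SAP 3.2, remove the whole-duration condition for the Safety Analysis Set and group by product received, for example: *A subject who received one or more doses of presatovir is summarised under presatovir; all other subjects are summarised under placebo.* This is a proposed rule for mixed exposure, consistent with the principle in Protocol 8.6 but not stated there, so SAP 7.7 should record it as a clarification. If the sponsor prefers the randomised-arm default, SAP 7.7 should declare and justify it as a departure.

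Add a listing of subjects who received both products, giving the onset of each event relative to the first presatovir dose.

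As a wording clean-up only, align the PP sentence in SAP 3.2 with SAP 3.1.3.

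The cost is one sentence, one line in the derivation of actual treatment, and one short listing. The data are already collected: Protocol 5.5 has sites record bottle number by subject and date, and the SAP plans drug administration and accountability listings. There is a small downside. If a placebo subject received presatovir in error only late, for instance on Day 17, events before that dose would be counted under presatovir. The onset listing makes those events visible.
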